4.2. Safety Population

Same as ITT population.

4.3. Pharmacokinetics (PK) Population

The pharmacokinetics population will include all patients who received at least 1 dose of ACE-536 during Study A536-06 and have sufficient serum ACE-536 values for PK analysis.

5. STATISTICAL METHODOLOGY

5.1. Definitions

Transfusion Status

For patients without treatment interruption, transfusion status (NTD or TD) will carry-over from the base study A536-04.

For NTD patients with treatment interruption, transfusion status will be reassessed prior to C1D1 of study A536-06. NTD patients with treatment interruption are defined as patients who require transfusion of < 4 units of RBCs over the 8 weeks prior to Cycle 1 Day 1 of study A536-06.

For TD patients with treatment interruption, transfusion status will carry-over from the base study A536-04.

Transfusion Dependent (TD) Defined in Base Study A536-04

Based on the protocol, TD patients are defined as those who required ≥ 4 units of RBCs every 8 weeks (confirmed over 6 months prior to study A536-04 Cycle 1 Day 1). For statistical programming purposes, a patient is defined as TD if the total RBCs is ≥ 11 units during 26 weeks on or prior to study A536-04 Cycle 1 Day 1.

Non-transfusion Dependent (NTD) Defined in Base Study A536-04

NTD patients are those who do not meet the above definition for TD. For statistical programming purposes, NTD patients are defined as those who received < 11 units of RBCs during 26 weeks on or prior to study A536-04 Cycle 1 Day 1.

Baseline

For patients who roll over to Study A536-06 without interruption, the baseline for Study A536-04 will be used as the baseline for Study A536-06 for all measurements, as further defined below. For patients who enter Study A536-06 with interruption, the baseline for Study A536-06 will be used, as further defined below. For assessments that are not scheduled to be done or with an inadequate data collection window at the beginning of Study A536-06, the baseline for Study A536-04 will be used as the baseline for Study A536-06.

Baseline Hemoglobin

Baseline hemoglobin will be the average of hemoglobin measurements within 28 days of Cycle 1 Day 1, excluding measurements within 14 days following RBC transfusion.

Baseline Transfusion Burden

Baseline transfusion burden will be calculated as the total amount of RBC transfusions during the 12 weeks on or prior to Cycle 1 day 1.

Baseline for Other Parameters

Baseline erythropoietin (EPO) is defined as the maximum test value within 28 days prior to Cycle 1 Day 1. For all other parameters, baseline is defined as the last observation on or prior to Cycle 1 Day 1.

Transfusion Unit Conversion

A transfusion amount reported in “mL” will be converted to “units” according to medical review.

End of Treatment (EOT)

Procedures and evaluations for the end of treatment visit should be performed 28 days (± 7 days) after the last dose of ACE-536.

Post-Treatment Follow-Up (PTFU)

The PTFU visit should occur 2 months (± 7 days) after the last dose of ACE-536. If a patient has a positive ADA result at the last visit, the patient may be asked to return for additional ADA testing every three months, until a negative result is obtained or the result is considered to be stabilized.

Long-Term Follow-Up (LTFU)

LTFU visits should occur beginning every 6 months (± 14 days) after the last dose of ACE-536 for 3 years after the last dose of ACE-536.

End of Study (EOS)

Procedures and evaluations for the end of study visit should be performed approximately 3 years after the last dose of ACE-536.

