5.2. General Considerations

Unless otherwise noted, continuous data will be summarized with the following descriptive statistics: number of observations (n), mean, standard deviation (STD), minimum, median, and maximum. Categorical data will be summarized with frequencies (n) and percentages (%). In cases where missing data cause percentages not to sum to 100, a missing data row will be provided. Percentages will use column totals as the denominator unless otherwise indicated. For time to event variables, the Kaplan-Meier curves will be presented if the number of patients is more than 5.

All study data will be included in study data listings. Missing data will generally be treated as missing, not imputed, unless otherwise stated.

Data summaries may also be presented for TD and NTD patients separately as specified. All summaries will be descriptive. No formal hypothesis testing is planned.

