5.7.2.5. Erythropoiesis Parameters

Erythropoiesis parameters include serum EPO levels, reticulocytes, nucleated RBCs, soluble transferrin receptor, hemoglobin electrophoresis, and folate.

EPO will be taken at Day 1 of Cycle 1, Days 1 and 8 of Cycles 5, 9, 13, 17, Day 1 of every 4 subsequent cycles until cycle 85, EOT, and EOS. Reticulocytes and nucleated RBCs will be taken at Screening, Days 1 and 8 of Cycles 1, 3, 5, 7, 9, 11, 13, 15, 17, Day 1 of Cycles, 2, 4, 8, 10, 12, 14, 16 and Cycles 18 to 87, EOT and EOS visits. Soluble transferrin receptor will be taken at Day 1 of Cycles 1, 5, 9, 13, 17, Day 1 of every 4 subsequent cycles until Cycle 85, EOT, and EOS. Hemoglobin electrophoresis will be taken at Day 1 of Cycles 1, 5, 13, 21, 29, 37, 45, 53, 61, 69, 77, EOT, and EOS. Serum folate will be taken at screening for patients with treatment interruption to confirm eligibility, and required at Day 1 of Cycles 1, 5, 13, 21, 29, 37, 45, 53, 61, 69, 77, and EOT.

Descriptive statistics of observed values, absolute and percentage change from baseline values at each post-baseline visit will be presented for all patients. Plots of erythropoiesis parameters for mean observed values, mean change, and mean percentage change from baseline over time will be presented.

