7.3. Appendix 3 - Schedule of Events for Study A536-04

	Screen	Treatment Period															Follow up period		
		Cycle 1				Cycle 2			Cycle 3			Cycle 4			Cycle 5			EOT ¹²	EOS ¹³
		C1D1 ₂	C1D8	C1D1 ₁	C1D1 ₅	C2D1 ^{2,15}	C2D8	C2D15	C3D1 ^{2,15}	C3D8	C3D15	C4D1 ^{2,15}	C4D8	C4D1 ₅	C5D1 ^{2,15}	C5D8	C5D15	Day 113 (± 7d)	Day 141 (± 7d)
	Day -28 to -1	Day 1	Day 8 (± 1d)	Day 11 (± 1d)	Day 15 (± 1d)	Day 22 (± 2d)	Day 29 (± 2d)	Day 36 (± 2d)	Day 43 (± 2d)	Day 50 (± 2d)	Day 57 (± 2d)	Day 64 (± 2d)	Day 71 (± 2d)	Day 78 (± 2d)	Day 85 (± 2d)	Day 92 (± 2d)	Day 99 (± 2d)	Day 113 (± 7d)	Day 141 (± 7d)
Informed consent	X																		
Inclusion/Exclusion	X	X																	
Medical history	X																		
QoL Questionnaires ¹⁹	X														X			X ²⁰	X
Physical examination	X	X ²³				X			X			X			X			X ²³	X ²³
Vital signs ¹	X	X	X		X	X	X	X	X	X	X	X	X	X	X	X	X	X	
ECG (12 lead)	X				X													X	
MRI (Liver Iron Content) ¹⁷	X ³																	X	
MRI for EMH masses and spleen ²⁴	X ³																	X	
DXA for BMD of total body, lumbar spine, and total hip ²⁴	X ³																	X	
Leg Ulcer Assessment ²⁵	X	X			X			X				X			X			X	X
Abdominal Ultrasound ²¹	X ³																	X	
ECHO, MUGA or cardiac MRI	X ³																		
6MWT ²⁴	X																	X	
Serum iron studies ⁴	X	X	X		X	X		X				X			X			X	X
Serum folate and B ₁₂	X				X			X				X			X			X	X
Erythropoietin levels	X	X			X			X				X						X	X
Hematology ⁵	X	X	X		X	X	X	X	X	X	X	X	X	X	X	X	X	X	
Peripheral blood smear	X	X			X			X				X			X			X	
Serum chemistry ⁶	X	X			X	X		X				X			X			X	X
Urinalysis and Urine Chemistry ⁷	X	X			X							X						X	X
Anti-drug antibody ¹⁶		X										X						X	X ¹⁶
PK collection		X	X	X	X	X	X					X	X	X	X	X	X	X	
PD Biomarkers ⁸		X			X			X				X			X			X	
Hemoglobin electrophoresis		X										X						X	
Globin mRNA sample		X										X						X	
Bone Biomarkers ⁹		X										X						X	
Pregnancy test/menstrual history ¹⁰	X				X			X				X			X			X	X ²²
Evaluate transfusion frequency/volume ¹¹	X	X			X			X				X			X			X	X
Concomitant medications and AEs	X	X	X	X	X	X	X	X	X	X	X	X	X	X	X	X	X	X	
Administer ACE-536 ¹⁸		X			X ¹⁴			X ¹⁴				X ¹⁴			X ¹⁴				

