¹ **Vital signs:** Weight, heart rate, systolic and diastolic blood pressure, respiration rate, and temperature (measured in degrees Celsius). Height is measured only at Screening. If at any visit the systolic blood pressure is \geq 150 mmHg, the diastolic blood pressure is \geq 95 mmHg, and/or the absolute increase in either measure from baseline is \geq 20 mmHg, perform one repeat of the blood pressure assessment after a minimum of 15 minutes.

² **Study procedures** must be done prior to administration of study drug.

³ Screening MRI for Liver Iron Content, MRI of the chest and abdomen for EMH masses and spleen (expansion cohort only), BMD by DXA (expansion cohort only), abdominal ultrasound of the spleen (if no prior splenectomy; dose escalation cohorts only) and ECHO, MUGA or cardiac MRI can be performed up to 56 days prior to C1D1. If performed as part of standard of care, it does not need to be repeated.

⁴ **Iron Studies:** Serum iron, TIBC, transferrin, soluble transferrin receptor, ferritin, and NTBI.

⁵ **Hematology:** RBC, WBC with differential, hemoglobin, hematocrit, haptoglobin (optional), reticulocyte count, platelet count, MCV, MCH, MCHC, RDW, and nRBCs. On dosing days, hematology values are to be drawn and resulted (up to 1 day) prior to C1D1 (see Protocol Section 10.8.1 Patient Dose Modification Rules). Historical hemoglobin values will be collected for 12 weeks prior to C1D1. Historical transfusion history will be collected for 12 months prior to Cycle 1 Day 1. Baseline hemoglobin will be the average of two measurements; one measure performed within one day prior to Cycle 1 Day 1 and the other performed during the screening period (Day -28 to Day -1). Note: For any RBC transfusions received during the study, collect hemoglobin value just prior to transfusion.

⁶ **Chemistry:** Sodium, potassium, chloride, carbon dioxide/bicarbonate (optional), AST, ALT, lactate dehydrogenase (LDH), total bilirubin, indirect bilirubin, alkaline phosphatase, blood urea nitrogen (BUN)/urea, creatinine, GGT, calcium, phosphorus, glucose, amylase, lipase, total protein, albumin, and uric acid.

⁷ **Urinalysis by dipstick analysis:** pH, specific gravity, protein, glucose, ketones, blood, leukocyte esterase, and nitrite, with microscopic examination if indicated. Microalbumin and creatinine will be performed by the central lab.

⁸ **PD Biomarkers:** Hepcidin, GDF15 and others to be determined.

⁹ **Bone Biomarkers:** BSAP and CTX.

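### Baseline EPO is a maximum but each later EPO is a single draw, so if the C1D1 draw counts, rollover patients tend to show a fall with no true change

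*SAP*

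**What the plan says.** SAP 5.1 (Baseline for Other Parameters) gives EPO its own rule: "Baseline erythropoietin (EPO) is defined as the maximum test value within 28 days prior to Cycle 1 Day 1". The next sentence sets the rule for the rest: "For all other parameters, baseline is defined as the last observation on or prior to Cycle 1 Day 1". The EPO sentence does not say whether a sample taken on C1D1 itself counts.

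Also under SAP 5.1, patients who enter A536-06 without interruption keep their A536-04 baseline, and interrupted patients get a new A536-06 baseline.

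After baseline, SAP 5.7.2.5 schedules single samples: "EPO will be taken at Day 1 of Cycle 1, Days 1 and 8 of Cycles 5, 9, 13, 17", then Day 1 of every fourth cycle, EOT and EOS. The tables show observed values and "absolute and percentage change from baseline values at each post-baseline visit will be presented for all patients". For the plots, "mean percentage change from baseline over time will be presented", alongside mean observed values and mean change. No maximum is taken after baseline.

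SAP 5.7.4 also uses baseline EPO to split patients at 200 IU/L in the erythroid response subgroups.

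**The concern.** The maximum of two noisy measurements is on average higher than either one. Setting a single later measurement against it produces an apparent fall without any drug effect. Such a fall could be read as improved erythropoiesis. It would also partly mask a true rise, and Protocol 7.3 reports small EPO increases in phase 1.

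The artefact would depend on entry route. Rollover patients can have two scheduled baseline draws and interrupted patients have one, so a pooled summary would depend partly on the mix of routes. The maximum also makes a rollover patient more likely to be placed in the subgroup at or above 200 IU/L.

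No reason for the maximum is given. The analysis section of the protocol (15.2.3) does not define it, and SAP 5.12.6, which lists the changed hemoglobin baseline, does not mention it.

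**Working it through.** **Number of scheduled baseline draws**

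- *Rollover patients.* In the A536-04 schedule (SAP Appendix 3), the row "Erythropoietin levels" is marked at Screening and at C1D1. Note 2 there says that study procedures "must be done prior to administration of study drug", so the C1D1 draw is pre-dose. There are two draws if C1D1 counts and one if it does not.
- *Interrupted patients.* The A536-06 schedule (SAP Appendix 4) has EPO at C1D1 but not at Screening. There is one draw if C1D1 counts and none if it does not.

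**Size of the artefact if C1D1 counts**

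The plan gives no figure to reproduce and no EPO variability. The following are assumptions: within-patient CV of 20, 30 or 50%; correlation between the two baseline draws of 0 or 0.5; lognormal values; an independent later draw; no true change.

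1. On the normal scale, the expected maximum of two independent draws exceeds the mean by 1/√π = 0.564 within-patient SD. At correlation 0.5 the excess is 0.564 × √0.5 = 0.399 SD.
2. With exchangeable continuous draws, the later value is the largest of three with probability 1/3. So 2/3 of rollover patients show a fall, against 1/2 with a single-draw baseline.
3. The log-scale SD is s = √ln(1 + CV²) = 0.198, 0.294, 0.472. For independent draws:
   - mean absolute change as a share of the true mean = 1 − 2Φ(s/√2);
   - geometric mean ratio = exp(−0.564 s), or exp(−0.399 s) at correlation 0.5;
   - arithmetic mean % change = 2·exp(s²)·Φ(−s/√2) − 1.
4. With a single-draw baseline, the arithmetic mean % change is exp(s²) − 1 = CV².

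Results at CV 20 / 30 / 50%, with medians from a lognormal simulation of 4,000,000 patients per setting:

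| Measure | Maximum, independent | Maximum, correlation 0.5 | Last value |
|---|---|---|---|
| Absolute change, % of true mean | -11 / -16 / -26 | -8 / -12 / -19 | 0 |
| Median % change | -10 / -15 / -23 | -8 / -11 / -17 | 0 |
| Geometric mean ratio, % | -11 / -15 / -23 | -8 / -11 / -17 | 0 |
| Arithmetic mean % change | -8 / -9 / -8 | -4 / -4 / +2 | +4 / +9 / +25 |
| Patients showing a fall | 67% | 62% | 50% |

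The first, second, third and fifth rows point the same way throughout. The arithmetic mean % change does not: for independent draws it turns positive once s exceeds about 0.68, because ratios are skewed.

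**Pooled table**

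The rollover share is also an assumption. For independent draws, the share showing a fall is f × 2/3 + (1 − f) × 1/2. At f = 25, 50 and 75% this is 54, 58 and 63%. The pooled median % change at CV 30% is then -4, -8 and -12%. Over CV 20 to 50% it runs from -3 to -7, from -6 to -13 and from -8 to -18%.

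**Subgroup label**

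If one draw reaches 200 IU/L with probability p, the maximum of two independent draws does so with probability 1 − (1 − p)².

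- True mean 150 IU/L: 6 v 12%, 13 v 24% and 20 v 36% at CV 20, 30 and 50%. For example, p = 0.130 gives 1 − 0.870² = 0.243.
- True mean 180 IU/L: 26 v 46%, 31 v 52% and 32 v 54%.
- Further from the cut, at CV 30%, the effect shrinks: 0.6 v 1.2% at 100 IU/L and 89 v 99% at 300 IU/L.

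**If C1D1 does not count**

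Rollover patients then have one scheduled draw, at Screening, and the bias disappears. Interrupted patients have no scheduled A536-06 EPO in the window. SAP 5.1 might send them to the A536-04 baseline through its fallback for assessments not scheduled at the start of A536-06, which is an inference. SAP 5.12.1 gives interrupted patients the last value before the first A536-06 dose. The two sections could then give different baselines. If C1D1 counts, they agree for these patients on the scheduled draws.

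**The case against.** The strongest objection concerns the wording. The EPO sentence stops at prior to C1D1, while the next sentence adds *on or*. Read literally, the contrast excludes C1D1, and with it the bias. A maximum could still serve to resolve repeat or unscheduled samples. This stands as a condition on the bias, but it does not rescue the text. On the scheduled draws it leaves the maximum with nothing to choose between, and it leaves interrupted patients without a scheduled A536-06 baseline EPO. Either reading needs a correction.

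Second, the remedy worsens one planned output. With the last value, arithmetic mean % change becomes +4, +9 and +25%. For independent draws that is smaller in size than under the maximum at CV 20%, about equal at 30% and about three times as large at 50%. At correlation 0.5 it is not better at any of the three CVs. This stands, and it is why the remedy must also cover how relative change is summarised.

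Third, the size is assumed throughout, and the subgroup shift is appreciable only near the cut. Both points stand. The direction of the absolute and median change does not depend on the assumed CV.

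Fourth, the maximum may be the A536-04 analysis rule. That cannot be checked from these documents. SAP 5.12.6 does align with that study elsewhere, so the mismatch is a real possible cost.

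Finally, SAP 5.12.1 refers back to 5.1 and is a loose summary, so it is weak support on its own for a last-value rule. The case does not rest on it.

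**Conclusion.** The concern holds, conditional on the C1D1 draw counting. In that case the EPO rule builds in a fall of about 0.56 within-patient SD for rollover patients (0.40 at correlation 0.5) and none for interrupted patients. The percentages rest on the assumed CVs, correlation and rollover share, and on treating each visit as one draw. SAP 5.12.1 leaves the analysis windows to programming specifications; Days 1 and 8 of a cycle are treated here as separate visits.

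The consequence is minor. It touches a descriptive secondary pharmacodynamic endpoint and one subgroup label. Observed EPO by visit is shown as well and does not use the baseline. The correction is still worth making because the artefact is systematic, differs by entry route and can be removed without new data.

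**What to change.** In SAP 5.1, state that pre-dose C1D1 values count. For EPO change from baseline, use the last value on or before C1D1, as for the other parameters in that paragraph. This also settles the ambiguity about C1D1 and brings the rule into line with SAP 5.12.1 for interrupted patients.

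For relative EPO change, rely on the median, which SAP 5.2 already includes in the tables ("mean, standard deviation (STD), minimum, median, and maximum"), or on a geometric mean ratio. Do not rely on the arithmetic mean % change, which a single-draw baseline biases upward. The planned plot of mean percentage change should show the median for EPO or carry a footnote. If the maximum is wanted for the 200 IU/L subgroup, define it separately for that use only.

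The cost is one sentence, one derivation line and one plot footnote. If the A536-04 analysis used the maximum, the same patients would have different EPO baselines in the two reports, which a further footnote can state.

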10.2.3. RBC Transfusions

Concurrent treatment for anemia with blood transfusions is allowed, at the discretion of the investigator, for low hemoglobin levels, symptoms associated with anemia (e.g., hemodynamic or pulmonary compromise requiring treatment) or comorbidity.

For any RBC transfusions (NTD or TD patients) received during the study, collect hemoglobin values just prior to transfusion.

Each TD patient will have a defined “pre-transfusion hemoglobin threshold” which will be calculated based on transfusion history and will be used for determining when to transfuse during the study. The baseline pre-transfusion hemoglobin threshold will be the mean of all documented pre-transfusion hemoglobin values during the 12 weeks prior to C1D1 of base study A536-04 (for patients without treatment interruption) or study A536-06 (for patients with treatment interruption). During treatment, if the pre-transfusion hemoglobin level is increased by ≥ 1 g/dL compared to the baseline pre-transfusion hemoglobin threshold for that patient, transfusion should be delayed by a minimum of 7 days and/or the number of units transfused should be reduced by 1 or more RBC units. Patients may be transfused at the investigator’s discretion for symptoms related to anemia or other requirements (e.g., infection). Patients may be transfused on the same day as ACE-536 is administered except on C1D1 for patients with treatment interruptions.

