15.2.3. Secondary Analysis

All efficacy analyses will be performed for the EE and mITT populations.

Efficacy will be evaluated by determining the proportion of β -thalassemia patients who have an erythroid response, defined as 1) a mean hemoglobin increase ≥ 1.0 g/dL or ≥ 1.5 g/dL over an 8-week or 12-week period as compared to baseline, not influenced by RBC transfusion in NTD patients or 2) $\geq 20\%$ or $\geq 50\%$ reduction in RBC transfusion burden over an 8-week or 12-week period as compared to the 8-week or 12-week period pretreatment in TD patients.

Baseline hemoglobin for NTD patients will be the average of two or more measurements performed during the screening period for base study A536-04 (for patients without treatment

interruption) or study A536-06 (for patients with treatment interruption). Hemoglobin measurements within 2 weeks following RBC transfusion will be excluded.

Transfusion burden for TD patients will be defined as the ratio of RBC transfusion units (or mLs) transfused during an interval divided by the duration of that interval, where the interval may be during the pretreatment period or the treatment plus follow-up period. The interval during the pretreatment period will be defined as the 8 or 12 weeks prior to Cycle 1 Day 1 of base study A536-04 (will also be analyzed using pretreatment period of study A536-06 for patients with treatment interruption). An interval during the treatment plus follow-up period will be defined as an 8-week or 12-week interval after Cycle 1 Day 1 of study A536-06.

The erythroid response, as defined above, will also be evaluated using other pre-treatment and on-treatment intervals and other % reductions in RBC units transfused, including 100% (transfusion-free).

The erythroid response will be summarized using both a point estimate and its exact 95% CI based on binomial distribution.

No direct comparison testing with concurrent or historical controls will be performed.

Analysis of other secondary efficacy/PD endpoints will include:

- Time to erythroid response and duration of erythroid response
- Change/percent change from pretreatment in mean transfusion burden in TD patients
- Change in mean hemoglobin level in NTD patients
- Change in pre-transfusion hemoglobin levels in TD patients (including analysis of patient subset with < 20% change in transfusion burden)
- Change from baseline in erythropoiesis parameters, including EPO, reticulocytes, nucleated RBCs, and soluble transferrin receptor

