Table 1: Examples of Possible Starting Dose with Dose Modifications (Reductions and Titrations)

3 rd Dose Reduction	2 nd Dose Reduction	1 st Dose Reduction	Starting Dose Level	1 st Dose Titration	2 nd Dose Titration
0.2 mg/kg	0.4 mg/kg	0.6 mg/kg	0.8 mg/kg	1.0 mg/kg	1.25 mg/kg
0.4 mg/kg	0.6 mg/kg	0.8 mg/kg	1.0 mg/kg	1.25 mg/kg	
0.6 mg/kg	0.8 mg/kg	1.0 mg/kg	1.25 mg/kg		

- Starting dose level for TD and NTD patients to be determined based on data from study A536-04 (range: 0.2-1.25 mg/kg).
- Starting dose level for patients without treatment interruption will be last dose level (rounded to nearest A536-06 starting dose level) administered in study A536-04 unless a dose reduction is required based upon patient dose modification rules from study A536-06.
- Patients may be titrated up and down dose levels as required per protocol to meet dose modification and titration rules.
- Patients who require more than 2 dose reductions due to an AE should be discontinued from treatment and complete the EOT and EOS visits.
- The maximum dose titration will not exceed the maximum dose level tested in base study A536-04.
- Each TD patient will have a defined “pre-transfusion hemoglobin threshold” which will be calculated based on transfusion history and will be used for determining when to transfuse during the study. The baseline pre-transfusion hemoglobin threshold will be the mean of all documented pre-transfusion hemoglobin values during the 12 weeks prior to C1D1 of base study A536-04 (for patients without treatment interruption) or study A536-06 (for patients with treatment interruption). During treatment, if the pre-transfusion hemoglobin level is increased by ≥ 1 g/dL compared to the baseline pre-transfusion hemoglobin threshold for that patient, transfusion should be delayed by a minimum of 7 days and/or the number of units transfused should be reduced by 1 or more RBC units. Patients may be transfused at the investigator’s discretion for symptoms related to anemia or other requirements (e.g., infection).

Patients will participate in the extension study A536-06 for up to 97 months, including a 28-day (1 month) screening period, a 60-month treatment period and a 3-year (36 months) follow-up period.

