5.7.2.3. Change of Hemoglobin Level and Transfusion Burden

The mean change in hemoglobin level from baseline over 8- or 12-week period in NTD patients and the mean % change from baseline in transfusion burden over an 8- or 12-week period in TD patients will be summarized. In addition, the mean change in pre-transfusion hemoglobin levels in TD patients (including analysis of patient subset with $< 20\%$ change in transfusion burden) will also be analyzed. Summary statistics will be presented for these parameters.

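### The SAP names no baseline for change in pre-transfusion hemoglobin in TD patients, so its catch-all rule literally supplies one last value instead of the 12-week mean

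*SAP*

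**What the plan says.** SAP 5.7.2.3 plans to summarise "the mean change in pre-transfusion hemoglobin levels in TD patients", including a subset whose transfusion burden changed by less than 20%. It gives neither a reference value nor an on-treatment window for this quantity. Protocol 15.2.3 lists the same endpoint and also gives no baseline for it.

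SAP 5.1 sets specific baselines for hemoglobin, transfusion burden and erythropoietin, and then closes with a residual rule: "For all other parameters, baseline is defined as the last observation on or prior to Cycle 1 Day 1". Pre-transfusion hemoglobin is not mentioned. The hemoglobin entry reads: "Baseline hemoglobin will be the average of hemoglobin measurements within 28 days of Cycle 1 Day 1, excluding measurements within 14 days following RBC transfusion".

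Elsewhere, both documents describe a pre-transfusion quantity with the word baseline in its name. SAP 3.1 says: "The baseline pre-transfusion hemoglobin threshold will be the mean of all documented pre-transfusion hemoglobin values during the 12 weeks prior to C1D1". The C1D1 meant is that of A536-04 for patients without treatment interruption and that of A536-06 for patients with interruption. Protocol 9.1, 10.2.3 and 12.1 give the same rule. Its stated use is operational: it "will be used for determining when to transfuse during the study".

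SAP 5.12.6, which lists changes from the protocol's planned analyses, records a revised baseline hemoglobin definition but no decision on pre-transfusion hemoglobin.

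**The concern.** A programmer who follows SAP 5.1 as written finds no entry for this endpoint and arrives at the residual rule, so each TD patient's baseline is one draw. The trial meanwhile already calculates an average of several such draws for the same patient. The less precise figure would enter the analysis by default, with nothing to show that anyone chose it.

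There is also a mismatch within SAP 5.7.2.3. The subset with less than 20% change in burden is selected on transfusion burden, whose SAP baseline covers 12 weeks. The hemoglobin change reported for that subset would be measured from a single draw.

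Finally, the data are open-label. An unstated baseline can be settled after the values have been seen. Writing it down before database lock removes that question.

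**Working it through.** No figure in the documents depends on this point, so there is nothing to reproduce. The check has two parts.

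**1. Which rule applies**

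| Candidate | Where | Fits the endpoint? |
|---|---|---|
| Last observation up to C1D1 | SAP 5.1, residual rule | Applies literally, since no specific entry exists |
| 28-day hemoglobin mean | SAP 5.1, hemoglobin entry | Not restricted by transfusion status, but SAP 5.4 and 5.12.6 and Protocol 15.2.3 tie baseline hemoglobin to NTD patients |
| 12-week mean of pre-transfusion values | SAP 3.1; Protocol 9.1, 10.2.3, 12.1 | Right quantity, but given as a transfusion threshold and not named as the analysis baseline |

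**2. Cost in precision of a single value**

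Assumptions, none of them given in the documents:
- The last observation is itself a pre-transfusion value.
- Values are independent, with within-patient SD *s*.
- Transfusions occur every 2, 3 or 4 weeks, so 12 weeks hold *k* = 6, 4 or 3 pre-transfusion values.
- The on-treatment mean uses *m* = *k* values.

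Formulas for the within-patient error SD of the change:
- last value as baseline: *s*·√(1 + 1/*m*)
- 12-week mean as baseline: *s*·√(1/*k* + 1/*m*)
- variance ratio with *m* = *k*: (1 + 1/*k*)/(2/*k*) = (*k* + 1)/2

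| Interval | *k* | SD, last value | SD, 12-week mean | SD ratio | Variance ratio |
|---|---|---|---|---|---|
| 2 weeks | 6 | 1.08*s* | 0.58*s* | 1.87 | 3.5 |
| 3 weeks | 4 | 1.12*s* | 0.71*s* | 1.58 | 2.5 |
| 4 weeks | 3 | 1.15*s* | 0.82*s* | 1.41 | 2.0 |

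Both baselines have the same expected value under these assumptions, so the mean change is not biased by the choice.

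These ratios concern within-patient error only. Real differences between patients in their true change add the same variance under either baseline and pull the ratio of observed SDs towards 1. For example, if true changes vary with SD equal to *s*, the variance ratio is (1 + 1 + 1/*k*)/(1 + 2/*k*). That gives 2.167/1.333 = 1.63 for *k* = 6, 2.25/1.5 = 1.50 for *k* = 4 and 2.333/1.667 = 1.40 for *k* = 3, or SD ratios of about 1.27, 1.22 and 1.18. Positive correlation between successive values would also reduce the advantage of averaging.

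**The case against.** **There is no contradiction between two endpoint definitions.** A reader might infer that the protocol fixes the 12-week mean as the endpoint's baseline and that SAP 5.1 overrides it. The documents do not support that. The 12-week mean is introduced to guide transfusion, Protocol 15.2.3 gives the endpoint no baseline, and SAP 5.1 never mentions pre-transfusion hemoglobin. One could even argue that SAP 3.1, as the more specific text, would be preferred over a residual rule. This objection stands against any claim of conflict. It does not remove the gap: nothing tells the programmer to take SAP 3.1 as an analysis rule, and SAP 5.1 is the section that says how baselines are derived.

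**A biased gain is not shown.** A reader might also infer that the 28-day hemoglobin mean would be used, which would mix mid-interval values with pre-transfusion values, raise the baseline and understate the gain. Take a linear fall, one value drawn on average midway between day 15 and the day before transfusion, and one pre-transfusion value. The rise is then ½·(3.5/21)·2.0 = 0.17 g/dL for a 21-day interval with a fall of 2.0 g/dL, and ½·(7/28)·2.5 = 0.31 g/dL for a 28-day interval with a fall of 2.5 g/dL. The arithmetic is sound, but every input is assumed and the reading is the less likely one. SAP 5.4 summarises baseline hemoglobin for NTD patients only, the protocol rule it replaces is for NTD patients, and SAP 5.12.6 describes it in those terms. The bias should not be claimed.

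**A fourfold loss of precision overstates the effect.** With four transfusions in 12 weeks, the error variance of the baseline alone is four times larger for one value than for the mean. The reported quantity is a change, for which the ratio in that case is 2.5.

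**The 12-week window may be incomplete for interrupted patients.** Their transfusion history since the A536-04 end-of-study visit is collected only where available. That visit falls 56 days after the last A536-04 dose, and C1D1 of A536-06 comes at least 28 days later. At the minimum gap, 56 + 28 = 84 days, so before visit windows are counted the 12 weeks reach back to the last A536-04 dose. This stands, and the definition needs a fallback.

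**The endpoint is minor.** It is descriptive, one of many secondary summaries, and no hypothesis is tested. This also stands and limits the weight of the point.

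**Conclusion.** The point holds as a missing analysis baseline for one secondary endpoint, whose literal default is less precise than a quantity the trial already requires for each TD patient. It is a matter of precision and consistency. The documents show neither a contradiction nor a bias.

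The within-patient error SD of the change is about 1.4 to 1.9 times larger with the last value than with the 12-week mean (variance ratio 2.0 to 3.5). This rests on independent values, a transfusion every 2 to 4 weeks, equal numbers of baseline and on-treatment values, and a last observation that is itself pre-transfusion. Spread between patients in true change would make the loss in the observed SD smaller.

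The primary safety objective is untouched. Erythroid response in TD patients is based on transfusion burden, so no response rate changes. The correction is worth making before database lock because it is cheap and closes an open choice.

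**What to change.** Add one entry to SAP 5.1 for baseline pre-transfusion hemoglobin in TD patients, for analysis use. It should be the average of every documented value taken before a transfusion in the 12 weeks leading up to C1D1 of A536-04 (patients without interruption) or of A536-06 (patients with interruption). Where the A536-06 window is inadequate, use the A536-04 baseline, as SAP 5.1 already allows for other assessments, and state what counts as inadequate.

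In SAP 5.7.2.3, cite that entry and compare it with the mean of pre-transfusion values over the matching on-treatment interval.

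The cost is one definition, one cross-reference and a small programming change. SAP Appendix 3 already provides for 12 weeks of historical hemoglobin before C1D1 of A536-04, and the protocol already requires the 12-week mean for each TD patient. For interrupted patients the supply of values depends on what was available, hence the fallback. The change concerns the analysis only and leaves the transfusion rules as they are.
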